4.4. End of Study Definition

The end of the study is defined as the date of the last visit of the last participant in the study.

A participant is considered to have completed the study if he/she has completed all periods of the study including the end of study (EoS)/early discontinuation (ED) visit and any follow-up visits, if applicable, depending on whether the participant rolls over to ARGX-113-1905 or continues the treatment-free follow-up period in ARGX-113-1904.

5. TRIAL POPULATION

Protocol deviations to recruitment and enrollment criteria, also known as protocol waivers or exemptions, are not permitted.

Participants who do not meet all the inclusion criteria or who meet any of the exclusion criteria will not be eligible to receive any trial medication.

The criteria for screening and enrollment are to be followed explicitly. If it is noted that a participant who does not meet 1 or more of the inclusion criteria and/or meets 1 or more of the exclusion criteria was inadvertently enrolled and dosed, the sponsor's designated contract research organization (CRO) medical monitor/sponsor's designee and the sponsor's medical director must be contacted immediately. The decision to discontinue a participant from the trial will be taken on a case-by-case basis, where safety and benefit/risk assessment will be considered.

5.1. Inclusion Criteria

Participants are eligible to be included in the trial only if all of the following criteria apply:

1. Ability to understand the requirements of the trial, to provide written informed consent (including consent for the use and disclosure of research-related health information), willingness and ability to comply with the trial protocol procedures (including required trial visits).
2. The participant is male or female, and aged from 18 years at the time of signing the informed consent form (ICF).
3. The participant has a clinical diagnosis of PV (mucosal, cutaneous, mucocutaneous) or PF that has been confirmed by cutaneous histology, positive DIF, and positive IIF and/or ELISA.
4. The participant meets 1 of the following profiles:
 - i. Newly diagnosed disease with PDAI activity score ≥ 15 (see Section 10.8) at baseline and naïve to treatment.
 - ii. Newly diagnosed disease with PDAI activity score ≥ 15 while receiving a first course of oral prednisone (or equivalent). According to clinical judgment, the participant has shown no significant improvement of PV or PF signs for at least 2 weeks before baseline and is considered fit to start prednisone treatment at 0.5 mg/kg qd at baseline.
 - iii. Experiencing flare with PDAI activity score ≥ 15 , a maximum of 4 years since disease onset, and off prednisone therapy \pm a conventional immunosuppressant (eg, azathioprine, cyclophosphamide, methotrexate, mycophenolate mofetil) or dapsone. Note: conventional immunosuppressants and dapsone must be discontinued before baseline.
 - iiii. Experiencing flare with PDAI activity score ≥ 15 , a maximum of 4 years since disease onset, and receiving a tapered dose of oral prednisone (or equivalent), provided that prednisone has been given at stable dose \pm a conventional immunosuppressant (eg, azathioprine, cyclophosphamide, methotrexate, mycophenolate mofetil) or dapsone for at least 2 weeks and participants are fit to start prednisone treatment at 0.5 mg/kg

- qd at baseline. Note: conventional immunosuppressants and dapsons must be discontinued before baseline.
- 5A. Contraceptive use by men and women should be consistent with local regulations regarding the methods of contraception for those participating clinical trials and:
- i. Male participants:
 - Male participants must agree to use acceptable method of contraception (as described in Appendix 5, Section 10.5.2.2) from signing the ICF until the last dose of IMP.
 - ii. Female participants:
 - Women of childbearing potential (defined in Appendix 5, Section 10.5.1) must:
 - have a negative serum pregnancy test at screening and negative urine pregnancy test at baseline before the IMP can be administered.
 - agree to use a highly effective or acceptable contraception method (as described in Appendix 5, Section 10.5.2.2), which should be maintained at minimum until after the last dose of IMP.
6. For Japanese participants enrolled in sites in Japan only: A Japanese participant is defined as a participant whose parents and 4 grandparents are Japanese, and who has Japanese nationality, was born in Japan, has not lived outside of Japan for a total of >10 years, and currently lives in Japan.

5.2. Exclusion Criteria

Participants are excluded from the trial if any of the following criteria apply:

1. Participant has a confirmed diagnosis of paraneoplastic pemphigus, drug-induced pemphigus, pemphigus vegetans, pemphigus erythematosus, or any other non-PV/non-PF autoimmune blistering disease.
2. Participants with mild disease severity as defined by PDAI activity score <15 at baseline.
3. Participants who show a significant improvement of PV or PF in the period from screening to baseline according to clinical judgment (eg, the participant has achieved DC or a substantial reduction in PDAI activity score during screening period).
4. The participant has been administered therapy(ies) other than oral prednisone, conventional immunosuppressants (eg, azathioprine, cyclophosphamide, methotrexate, mycophenolate mofetil) or dapsons within 2 months before the baseline visit and that can affect clinical disease activity. For example, excluded medications are intravenous methylprednisolone, sulfasalazine, tetracyclines, nicotinamide at doses above the recommended daily allowance (RDA)/dietary reference intake (DRI), plasmapheresis/plasma exchange, immunoabsorption, and IVIg. Note: conventional immunosuppressants and dapsons must be discontinued before baseline. Nicotinamide doses at or below RDA/DRI from oral supplements is allowed.
5. Use of any monoclonal antibody (including rituximab or another anti-CD20 biologic) within 6 months before the baseline visit.

6. Known hypersensitivity to any of the components of the administered treatments.
7. The participant has a known contraindication to oral prednisone.
8. The participant has a history of refractory disease, as defined by a failure to respond to first-line and second-line therapies.
9. Participants who have a history of malignancy unless deemed cured by adequate treatment with no evidence of recurrence for ≥ 3 years before first IMP administration. Participants with any of the following cancers can be included at any time, provided they are adequately treated prior to their participation in the study:
 - i. Basal cell or squamous cell skin cancer
 - ii. Carcinoma in situ of the cervix
 - iii. Carcinoma in situ of the breast
 - iiii. Incidental histological finding of prostate cancer (TNM stage T1a or T1b)
10. Participants with clinical evidence of other significant serious disease or participants who recently underwent or have planned a major surgery during the period of the trial, or any other condition in the opinion of the investigator, that could confound the results of the trial or put the participant at undue risk.
11. Pregnant and lactating women and those intending to become pregnant during the trial.
12. Current or history (ie, within 12 months of screening) of alcohol, drug, or medication abuse.
13. Any other known autoimmune disease that, in the opinion of the investigator, would interfere with an accurate assessment of clinical symptoms of PV or PF or put the participant at undue risk.
14. The participant has a Karnofsky performance score $< 60\%$ (see Section 10.9).
15. Vaccination with live/attenuated viral vaccines within 28 days prior to randomization (see Section 8.3.7).
16. The participant has clinically significant uncontrolled active or chronic bacterial, viral, or fungal infection.
17. Positive serum test at screening for an active viral infection with any of the following conditions (refer to Section 10.2.1):
 - i. Hepatitis B Virus (HBV) that is indicative of an acute or chronic infection, unless associated with a negative HBV DNA test.
(<https://www.cdc.gov/hepatitis/HBV/PDFs/SerologicChartv8.pdf>; refer to Table 8).
 - ii. Hepatitis C Virus (HCV) based on HCV antibody assay (unless associated with a negative HCV mRNA test; refer to Section 10.2.1.2).
 - iii. HIV based on test results that are associated with an AIDS-defining condition or a CD4 count ≤ 200 cells/mm³ (refer to Table 9).
18. The participant has total IgG < 6 g/L at screening.

19. The participant has previously participated in a trial with efgartigimod and has received at least 1 administration of IMP.
20. Use of an investigational drug within 3 months or 5 half-lives of the drug (whichever is longer) prior to first IMP administration.
21. For Chinese participants enrolled in China only: Use of complementary therapies, including traditional Chinese medications, herbs, or procedures (eg, acupuncture) within 4 weeks prior to randomization, that can potentially interfere with the efficacy assessments and the safety of the participant, as assessed by the investigator.

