^f Trial visit windows are ±2 days during the treatment period and ±3 days for follow-up visits.

- ^g No trial-related assessments can be initiated before the participant has provided a signed ICF.
- ^h Only required if not available from medical history.
- ⁱ Height and weight will be measured (and BMI will be calculated accordingly) at screening, at week W15 (or the next on-site visit if W15 does not coincide with an on-site visit), and EoS/ED. Weight will also be measured if there has been an obvious change since the last measurement.
- ^j At visits in which IMP is administered, the assessment or procedure should be completed before dosing.
- ^k A complete physical examination will be completed at each on-site visit. Vital sign measurements include systolic and diastolic blood pressure, heart rate, and body temperature. Supine blood pressure and heart rate will be measured using standard equipment after at least 10 minutes rest.
- ^l ECG to be taken at W12. If the W12 visit does not coincide with an on-site visit, then the assessment should be performed at the next on-site visit. ECG (heart rate, PR, QT, and QRS interval) will be read centrally. QTcF and QTcB will be calculated.
- ^m Randomization will take place on day 1 after all eligibility checks are confirmed (eg, PDAI) and before other baseline assessments are run, and prior to dosing.
- ⁿ Urinalysis will be performed by dipstick method and will include specific gravity, pH, protein, glucose, ketones, blood, bilirubin, urobilinogen, nitrite, leukocyte esterase, and microscopic examination (if blood or protein test results are abnormal).
- ^o Samples will be taken every week from V1(BL)/W1 to W9 and then every 4 weeks and at the visit where CR is observed. Once CR is achieved, samples will be taken every 4 weeks at on-site visits until EoS/ED. For participants achieving CR between V1(BL)/W1 and W6, samples will be taken weekly from W1 to W6 and then every 4 weeks at on-site visits until EoS/ED.
- ^p A urine pregnancy test will be conducted and analyzed locally during on-site visits at least once every 4 weeks (before and after CR) and at the time of CR.
- ^q Viral testing for hepatitis B surface antigen (HBsAg), hepatitis B surface antibody (anti-HBs), hepatitis B core antibody (anti-HBc), hepatitis B virus (HBV) DNA, hepatitis C virus (HCV) antibodies, HCV messenger RNA (mRNA), and human immunodeficiency virus (HIV) antibodies.

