8.3.7. Infections and Vaccinations

Pemphigus patients are prone to develop infections. They include infections of the bronchi (bronchitis) and the lung (pneumonia), resulting from the mucosal pemphigus lesions of the upper respiratory tract, infections of the mouth and ear-nose-throat (ENT) system, superinfections of the skin, and infections of the genital and urinary tract. Concomitant and historical treatments by non-targeted therapies (corticosteroids, immunosuppressants) or targeted therapies (rituximab) are co-morbidity factors able to trigger or aggravate these infections.

In this trial, some measures able to mitigate the occurrence of infections are required, and other precautionary measures optimizing the prevention of infections are recommended. For these reasons, the following actions are excluded for trial entry (refer to Section 5.2):

- the administration of live/attenuated vaccines (eg, measles, mumps, rubella, rotavirus, smallpox, chickenpox, yellow fever) within the 4-week period prior to baseline visit (exclusion criterion 15) or during the trial.
- participants with an active or uncontrolled bacterial, viral, or fungal infection at screening (exclusion criterion 16).
- Participants that tested positive for an active viral infection at screening with HBV type B or type C, and HIV (exclusion criterion 17).
- participants with hypogammaglobulinemia, ie, total IgG <6 g/L (exclusion criterion 18).

The following measures prior to and during the study are highly recommended:

- To initiate or renew administration of non-live, inactivated, polysaccharide or recombinant vaccines (eg, tetanus, hepatitis A, hepatitis B, shingles) in participants susceptible to enter the trial, at least 4 weeks before baseline visit.
- To vaccinate participants that are especially prone to or with an history of respiratory infections against *Pneumococcus* or *Streptococcus pneumoniae*.
- To vaccinate pemphigus participants with seasonal vaccines (eg, influenza virus), especially those susceptible to enter the trial in the winter months.
- To screen for possible infections (eg, respiratory, skin, mouth, eyes, nose and throat, genitals) and, if appropriate, initiate antibiotic treatment before baseline visit.
- To provide participants suffering from recurrent episodes of herpes simplex or herpes zoster with antiviral treatment throughout the trial treatment.

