10.2.1. Other Screening Tests

10.2.1.1. Hepatitis B Virus

Patients with an active acute or chronic hepatitis B viral (HBV) infection at screening cannot be enrolled in the trial.

The following combinations of serologic markers will be used to identify an active HBV infection (<https://www.cdc.gov/hepatitis/HBV/PDFs/SerologicChartv8.pdf>):

Table 8: Interpretation of Hepatitis B Serological Test Results

Test Result			Interpretation
HBsAg	Anti-HBc	Anti-HBs	
Positive	Positive	Negative	The patient cannot be enrolled in the trial because the test results indicate an active HBV infection.
Negative	Positive	Negative	The patient cannot be enrolled in the trial because the test results indicate a low-level chronic HBV infection with impaired liver function. ^a

anti-HBc=total hepatitis B core antibody; anti-HBs=hepatitis B surface antibody; HBsAg=hepatitis B surface antigen; HBV=hepatitis virus

^a This decision will be made by a medical doctor with sufficient experience in hepatology or infectious disease. Additional tests (eg, HBV viral load) may be required to determine the status of the participant.

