10.2.1.2. Hepatitis C Virus

Patients with an active acute or chronic hepatitis C viral infection at screening cannot be enrolled in the trial. Patients with positive serology for hepatitis C virus antibody should not be enrolled unless associated with a negative HCV mRNA test.

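### Exclusion 17.i lets in HBV-DNA-negative patients, but Table 8 row 1, which it cites, bars one such pattern with no DNA condition, and the protocol does not say which text decides

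*Protocol*

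**What the plan says.** Criterion 17 in Protocol Section 5.2 excludes patients whose screening serum tests show an active viral infection, and refers to Section 10.2.1. Its hepatitis B limb, 17.i, covers a result "that is indicative of an acute or chronic infection, unless associated with a negative HBV DNA test" and refers to Table 8.

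Section 10.2.1.1 contains Table 8. It bars active acute or chronic hepatitis B and then says how that is recognised: "The following combinations of serologic markers will be used to identify an active HBV infection". The table has two rows, and both refuse enrolment.

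- **Row 1** (HBsAg positive, anti-HBc positive, anti-HBs negative): "The patient cannot be enrolled in the trial because the test results indicate an active HBV infection".
- **Row 2** (HBsAg negative, anti-HBc positive, anti-HBs negative): refused as a low-level chronic infection, with footnote a attached.

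Footnote a leaves the decision to a physician experienced in hepatology or infectious disease and adds: "Additional tests (eg, HBV viral load) may be required to determine the status of the participant". In the text available for this review, it is marked on row 2 only.

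For hepatitis C, the criterion and its appendix agree. Criterion 17.ii has an exception for a negative RNA test, and Section 10.2.1.2 repeats it: "Patients with positive serology for hepatitis C virus antibody should not be enrolled unless associated with a negative HCV mRNA test".

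**The concern.** A criterion and the table it cites should give the same answer for the same screening result. Here they can differ, because the criterion has a negative-DNA exception and row 1 of the table has none.

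This is a safety eligibility rule. Under Section 6.8.1 every participant starts prednisone at 0.5 mg/kg daily, with escalation allowed to 1.5 mg/kg. With 2:1 randomization, two thirds also receive a drug that lowers IgG. Viral testing is scheduled at screening only, so the entry rule is where hepatitis B status is settled. One site could enrol a patient on the strength of 17.i while another refuses the same patient under Table 8. A site that enrols could also be told that it breached the table.

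**Working it through.** No arithmetic applies. The check is to put each screening pattern in Table 8 through both texts.

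**Inputs.** Criterion 17.i (Section 5.2); Section 10.2.1.1 with Table 8 and footnote a; the screening viral panel (Section 1.3, Table 1 footnote q, and Section 10.2, Table 7); the general rule on applying criteria (Section 5).

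**Can the case be seen at screening?** Yes. Footnote q lists HBsAg and anti-HBs together with "hepatitis B core antibody (anti-HBc), hepatitis B virus (HBV) DNA", so a site would hold both the serology and the DNA result.

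**Side by side**

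| Screening result | Criterion 17.i | Table 8 | Same answer? |
|---|---|---|---|
| HBsAg+, anti-HBc+, anti-HBs−, DNA positive | Excluded | Row 1: refused | Yes |
| HBsAg+, anti-HBc+, anti-HBs−, DNA negative | Not excluded | Row 1: refused, no DNA condition | **No** |
| HBsAg−, anti-HBc+, anti-HBs−, DNA positive | Excluded, if this serology counts as indicating infection | Row 2: refused, subject to footnote a | Compatible |
| HBsAg−, anti-HBc+, anti-HBs−, DNA negative | Not excluded | Row 2: refused by default, but a specialist decides and may use viral load | Can be reconciled through footnote a |

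Only the second line gives opposite answers with no stated way to reconcile them.

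**Does another passage settle it?** Section 5 makes anyone who meets an exclusion criterion ineligible, allows no waivers and tells sites to apply the criteria to the letter. It sets no order between Section 5.2 and Appendix 2. Section 8.3.7 also mentions hepatitis B, but it only points back to criterion 17 and shortens the hepatitis C and HIV rules in the same way, so it supports neither side.

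**Is the missing exception just appendix style?** The hepatitis C subsection suggests not. The same appendix restates the negative-RNA exception there. In the hepatitis B subsection, viral load appears only in footnote a.

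**The case against.** The strongest reply is that the two texts fit together. Eligibility turns on the numbered criteria, and Table 8 is titled as an aid to interpreting serology. On this view 17.i has two steps: Table 8 says whether the serology indicates infection, and 17.i then releases the patient if DNA is negative. The presence of HBV DNA in the screening panel fits that intention. This is a reasonable reading, so the texts should not be called irreconcilable. But the protocol does not state it, and row 1 does more than interpret serology: it gives an enrolment decision.

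A second reply is that the placement of footnote a may be an artefact of reading the PDF. If the published table marks both rows, row 1 also becomes a specialist decision and the conflict softens. An automatic exemption in 17.i would still sit beside a case-by-case decision in the table.

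A third reply is that other controls limit the risk, and this is fair:

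- criteria 10 and 16 let the investigator exclude for undue risk or for clinically significant uncontrolled infection;
- eligibility is reviewed by the CRO and medical monitors (Section 10.1.7.3);
- liver tests are routine (Section 1.3), with follow-up of significant abnormalities (Section 8.3.6);
- Section 8.3.7 allows preventive measures to be discussed with the medical monitor before entry;
- the DSMB reviews unblinded safety data (Section 10.1.5.1).

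These controls mitigate the risk, but none says which hepatitis B rule applies.

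A reader might also infer that the plan knowingly exposes patients to viral reactivation. The documents do not support that. They say nothing about reactivation risk in a DNA-negative patient on prednisone or efgartigimod, and they leave room for preventive measures.

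**Conclusion.** The mismatch is real and narrow. For an HBsAg-positive, anti-HBc-positive, anti-HBs-negative patient with negative HBV DNA, criterion 17.i does not exclude and Table 8 row 1 refuses, and no passage says which decides. Row 2 is not in the same position, because footnote a supplies a route. A site that declines the row 1 patient breaches neither text, so the exposure is limited to a site that enrols on 17.i alone.

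Severity is minor. The number of such patients is not in the documents. A reader might infer consequences for power, the per-protocol set or the primary result. Nothing in the documents supports this, because the conflict concerns who may enter and touches no sample-size or analysis rule.

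The conclusion rests on one assumption about the source: that footnote a is attached to row 2 only, as in the supplied text.

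**What to change.** State one rule and use it in both criterion 17.i and Section 10.2.1.1 with Table 8. There are two ways to do this.

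- **Safer default.** Limit the negative-DNA exception in 17.i to the row 2 pattern (HBsAg negative, anti-HBc positive, anti-HBs negative), subject to the footnote a specialist decision. Row 1 stays as written. The cost is possibly a few more screen failures; the documents do not allow a count.
- **If the wider exception is intended.** Add the negative-DNA condition to Section 10.2.1.1 and to Table 8 row 1, as Section 10.2.1.2 already does for hepatitis C. This changes no one's eligibility under 17.i and removes the bar that contradicts it.

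The choice is clinical and belongs to the sponsor. Either way the work is a short protocol clarification, with no change to the SAP.

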5.3. Lifestyle Considerations

No lifestyle restrictions are required.

5.4. Screen Failures

Screen failures are defined as participants who consent to participate in the clinical trial but are not subsequently randomly assigned to trial intervention. A minimal set of screen failure information is required to ensure transparent reporting of screen failure participants to meet the Consolidated Standards of Reporting Trials (CONSORT) publishing requirements and to respond to queries from regulatory authorities. Minimal information includes demography, screen failure details, eligibility criteria, and any SAE.

Participants may be rescreened (ie, redoing the full assessments), per the SoA (Section 1.3) or retested once (ie, redoing 1 assessment) after the sponsor's written approval.

Examples of conditions under which retesting may be considered include the following:

- Participants who have clinical laboratory test values meeting 1 or more exclusion criteria that are not in line with the medical history and clinical evaluation of the participant, may be retested to confirm the value of the tests, if still allowed within the screening period. If not feasible, the participant should be rescreened.

Participants may be rescreened once under the following conditions:

- Participants who required treatment for an acute illness that resolved (eg, a urinary tract infection) or had stabilization of a chronic medical problem (eg, uncontrolled hypertension).
- Participants who are not on a stable dose of a concomitant medication prior to randomization as per inclusion and exclusion criteria may be rescreened once the stable dose criterion is met.

The decision to rescreen participants may be optional based on clinical state of the participant and the decision to rescreen will solely be made per the sponsor's discretion on a case-by-case basis. For the purpose of rescreening, a new ICF should be completed.

